2.2.1 Subgroup of interest

The following subgroups will be used for descriptive summary of the selected efficacy and safety analyses in all cohorts pooled. The details will be provided in the corresponding sections.

- Age groups as per Section 2.3
- Baseline weight groups as per section 2.3
- Sex (male vs female)

2.3 Patient disposition, demographics and other baseline characteristics

2.3.1 Medical history

Any condition entered on the *Relevant medical history / current medical conditions* CRF will be coded using the MedDRA dictionary. They will be summarized by system organ class (SOC) and preferred term (PT) of the MedDRA dictionary. Summary will also be provided on medical conditions that were active at the time of screening.

Medical conditions that are present after informed consent has been signed are collected in the Adverse event panel and will be summarized separately from adverse events if considered necessary.

Unless otherwise specified, analyses will be based on the randomized set.

2.3.2 Patient demographics and other baseline characteristics

Demographic data and baseline disease characteristics will be descriptively presented and tabulated per treatment group, as well as overall, using FAS and PPS. If there are patients in the SAF excluded from FAS, summary will also be provided for the SAF.

Following demographic variables will be summarized

- Age and age categories (6 months to < 2 yrs, 2 to <6 yrs, 6 to <12 yrs, 12 to <18 yrs)
- Sex (male, female)
- Race (White, black, Asian, native American, pacific islander, unknown, other)
- Ethnicity
- Body weight and weight categories (5 to <10, 10 to <15, 15 to <25, 25 to <35, 35 to <55, 55 to <75, and ≥ 75 kg)
- Body height (cm)
- BMI and BMI categories (<16, 16 to 25, >25) (Kg/m²)

Following disease characteristics at baseline will be summarized

- Body temperature and categories equivalent to axillary method (<37.5, 37.5 to <38.5, ≥ 38.5) (°C)
- Falciparum species: (P. Falciparum asexual forms, [REDACTED], P. Vivax, P. Ovale, P. malariae, P. Knowlesi, and Mixed-infection, n (%))
- P. falciparum density per micro ltr. and its categories (<1,000, 1,000 to <2,000, 2,000 to <5,000, 5,000 to <15,000, 15,000 to <50,000, 50,000 to <100,000, 100,000 to <150,000, $\geq 150,000$ parasites/ μ L; <100,000 / μ L, $\geq 100,000$ parasites / μ L)

[REDACTED]

2.3.3 Patient disposition

The number of patients who screened and screening failures will be presented. In addition, the reasons for screen failures will be provided. The number and percent of patients who completed or discontinued the treatment and study (including the reason for discontinuation) will be presented for each treatment group and overall.

For each protocol deviation, the number and percent of patients for whom the deviation applies will be tabulated.

Randomized set will be used.

2.4 Treatments (study treatment, compliance, rescue medication, concomitant therapies)

2.4.1 Study treatment / compliance

Number and percent of patients with study drug vomiting and successfully receiving replacement dose will be presented by treatment group. A patient is called as receiving successful replacement dose if the patient does not vomit the replacement dose.

Overall compliance for each study drug will be calculated separately using following formula: (sum of full doses taken/ sum of planned doses) x100 %. For KAF/LUM, compliance for combined dose will be the average compliance of both drugs. Compliance will be categorized by < 80 % and ≥80 % of planned doses taken and summarized by treatment group.

For e.g., if a patient from KAF 400/LUM 480 QD x 2 took 400 mg of KAF on Day 1 and 200 mg of KAF on Day 2 then overall compliance for KAF is $600/800 \times 100\%$ which is equal to 75%. If the patient receives 480 mg of LUM on both days, then the overall compliance for LUM is 100%. The average compliance for KAF/LUM combination for this patient is $(75\% + 100\%) / 2 = 87.5\%$

Note- If a patient vomited the original dose but did not vomit the replacement dose, the patient is considered as fully dosed. If a patient vomited the original dose and did not have a replacement dose or vomited both the original dose and the replacement dose, the patient is not considered as fully dosed.

Safety set will be used.

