2.2 Analysis sets

Randomized set

All patients who are randomized into the study.

Full analysis set (FAS)

FAS will be comprised of all patients from Randomized set who take at least one dose of study treatment during the treatment period and whose baseline *P. Falciparum* asexual parasitaemia count is greater than 0. Following the intent-to-treat principle, patients will be analyzed according to the treatment group assigned to at randomization.

Unless otherwise specified, misrandomized patients will be excluded from the FAS.

Misrandomized patients, if identified from IRT, include patients who are screen-failures, but have been randomized by the investigator before eligibility was finally assessed or mistakenly, and have not been treated. If patients were re-screened and successfully randomized, they will be included in the randomized set according to the treatment assigned in the last randomization.

Safety set (SAF)

Safety set includes all patients who take at least one dose of study drug during the treatment period. Patients will be analyzed according to treatment received. In particular, patient will be analyzed in the same treatment group as randomized if s/he receives at least one dose of the study medication of that group. For the PK run-in cohort, all patients to receive the same dose in either fasted or fed condition.

Per-protocol set (PPS)

Per-protocol set will be comprised of patients in FAS who

- did not have any important protocol deviations affecting efficacy
- took at least 80% dosages of randomized study medication(s). If a patient vomited the original dose but did not vomit the replacement dose, the patient is considered as taking the dose of study medication. Since a partial compliance, such as 83%, etc., can be calculated based on the actual dosage taken (see [Section 2.4.1](#)), this allows patients to take partial dosages.
- did not take non-study medications with anti-malaria activity prior to Day 29 visit unless experiencing any treatment failure (ETF, LCF, LPF) (e.g new infections between Day 8 and Day 29), and PCR corrected ACPR status at Day 29 is defined, ie, at least one of the following criteria is met:
 - a. classified as treatment failure before Day 8 (see [Section 2.1.1](#))
 - b. had parasitaemia present on Day 8 or later without parasite clearance before (eg., parasite present Day 15 and parasite was not cleared before Day 15).
 - c. absent from parasitaemia at Day 29 or later,

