 - d. had a recrudescence if parasitaemia is present from Day 8 to Day 29, or
 - e. had a new infection at Day 29 visit or later

Food noncompliance in the Run-in cohort is considered as important PD. Important protocol deviations for exclusion from PPS are specified in [Table 5-14](#) and will be identified by the clinical team before the database lock.

PK analysis set

Run-in Cohort

PK Analysis set: All the subjects in the safety analysis set who have at least one evaluable PK concentration. A profile is considered evaluable for that period if following conditions are satisfied:

- Participants took at least 80% dosages of randomized study medication
- If a patient vomited the original dose but did not vomit the replacement dose
- Participants with no protocol deviations (PD) that may have an impact on the PK data

PK analysis set-partial food compliance: all subjects in the PK analysis set who are compliant to meal criteria (within 30 minutes of drug administration and took at least 70% of the standard meal) on any of the two dosing days.

PK analysis set-Full food compliance: all subjects in the PK analysis set who are compliant to meal criteria (within 30 minutes of drug administration and took at least 70% of the standard meal) on both dosing days.

Note that meal non-compliance for the run-in cohorts is identified using the PD (protocol deviation) code OTH04.

Cohort 1 and Cohort 2

PK Analysis set: All the subjects in the safety analysis set who have at least one evaluable PK concentration. A profile is considered evaluable for that period if following conditions are satisfied:

- Participants took at least 80% dosages of randomized study medication
- If a patient vomited the original dose but did not vomit the replacement dose
- Participants with no protocol deviations (PD) that may have an impact on the PK data

PK analysis set-partial food compliance*: all subjects in the PK analysis set who are compliant to meal criteria (within 1 hour (± 5 min) of drug administration and took at least 70% of light meal) on both Days 2 and 3.

PK analysis set-Full food compliance*: All subjects in the PK analysis set who are compliant to meal criteria (within 1 hour (± 5 min) of drug administration and took at least 70% of light meal) on all three dosing days.

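### Averaging KAF156 and LUM-SDF compliance lets a child with as little as 60% of one drug count as per-protocol in the primary non-inferiority test

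*SAP*

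**What the plan says.** SAP 2.4.1 starts drug by drug: "Overall compliance for each study drug will be calculated separately using following formula", namely doses taken over doses planned. For the two-product arm it then adds that "compliance for combined dose will be the average compliance of both drugs", and it sets the cut: "Compliance will be categorized by < 80 % and ≥80 % of planned doses taken and summarized by treatment group".

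The PPS definition in SAP 2.2 admits patients who "took at least 80% dosages of randomized study medication(s" (the closing bracket falls outside the quote) and explains that partial intake counts: "Since a partial compliance, such as 83%, etc., can be calculated based on the actual dosage taken". It refers to Section 2.4.1 for that calculation. Table 5-14 repeats the exclusion below 80%. Neither place states a minimum for each drug. SAP 2.5.2 tests the primary hypothesis on the PPS.

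For the PK analysis set, SAP 2.2 says "Participants took at least 80% dosages of randomized study medication", without pointing to 2.4.1. Table 5-14 instead removes from the PK set anyone whose compliance is below 100%. Protocol 12.1 uses 80% for both sets and has no averaging rule. SAP Section 4 declares no change from the protocol's analyses.

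**The concern.** KAF156 tablets and LUM-SDF sachets are separate products, given one after the other within 15 minutes (protocol 6.7.2). One can be refused, spat out or partly swallowed while the other is taken in full, and the dosing record is meant to capture whether all or part was swallowed (protocol 6.6.1). An average lets full intake of one drug hide a shortfall in the other. Coartem is a fixed-ratio tablet, so 80% of it is 80% of both components. Component by component, the criterion is therefore looser in the KAF156/LUM-SDF arm.

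A per-protocol set is meant to show how the planned combination performs in children who received it. A child who had about two thirds of one component is not such a child, whatever the outcome. What is at stake is how the PPS result can be read, not a demonstrated shift in the estimate.

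**Working it through.** **1. Reproduce the SAP's figure.** The example child on a two-day 400/480 mg regimen took "400 mg of KAF on Day 1 and 200 mg of KAF on Day 2" and all of the LUM-SDF.

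- KAF156: (400 + 200)/800 = 75%
- LUM-SDF: (480 + 480)/960 = 100%
- Combined: (75% + 100%)/2 = 87.5%, matching the SAP. The child stays in the PPS, although KAF156 alone is below 80%.

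**2. Find the floor.** Passing requires (K + L)/2 ≥ 80%, so the lower drug must reach at least 160% minus the other.

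| Other drug | Lowest passing value |
|---|---|
| 100% | 60% |
| 95% | 65% |
| 90% | 70% |
| 80% | 80% |

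The 60% floor applies only if the other drug is complete. At 59.9% with 100% the average is 79.95%, which fails.

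**3. Whole missed doses of one drug, the other complete.**

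- Two-day regimen, 1 of 2 doses: (50% + 100%)/2 = 75%, fails.
- Three-day regimen, 2 of 3 doses: (66.7% + 100%)/2 = 83.3%, passes.
- Three-day regimen, one day of both drugs missed: 66.7%, fails.

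In a two-day regimen only a partly taken dose can use the gap. In a three-day regimen one wholly missed dose of one drug is enough. The protocol leaves both durations open for Cohorts 1 and 2, and the SAP 2.2 food-compliance subsets for those cohorts refer to three dosing days.

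**4. Formula against example.** The SAP 2.4.1 formula counts doses taken in full; the example credits a half dose in mg. Read literally, the example child has 1 of 2 full KAF156 doses, so (50% + 100%)/2 = 75%, and leaves the PPS. By the mg method the same child scores 87.5% and stays.

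**5. Effect of one child.** The plan is 92 evaluable per arm at 95% (SAP 3.1.1). As an illustration, take 87 responders of 92 = 94.57%.

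- Remove one non-responder: 87/91 = 95.60%, up 1.0 percentage point.
- Remove one responder: 86/91 = 94.51%, down 0.06 point.

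The margin is 10 points.

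**6. PK set.** SAP 2.2 and protocol 12.1 admit at 80%; Table 5-14 excludes below 100%. The averages above (80.0%, 83.3%, 87.5%) all fail Table 5-14. Under the 80% text the outcome is unclear, because that text does not say whether the average applies.

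**The case against.** Several counter-arguments have force.

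- **Direction.** A reader might infer a bias towards non-inferiority. The documents do not support that. If under-dosing lowers response, keeping these children lowers the KAF156/LUM-SDF rate and makes non-inferiority harder to show. Removing them is the step that could favour the test arm. This stands.
- **PK.** A reader might also infer that the 60% child's concentrations are summarised as full-dose exposure. Table 5-14 would exclude that child from the PK set. The PK defect is the conflict between the two thresholds.
- **Per-drug information.** It might seem that averaging loses it. It does not: SAP 2.4.1 calculates each drug separately, and protocol 12.3 summarises doses and dosage by drug.
- **Few cases.** Dosing is supervised with a mouth check. A child who vomits the replacement dose is to receive alternative treatment (protocol 6.7.2), and non-study antimalarials during the treatment period lead to PPS exclusion (Table 5-14). What remains is mainly partly swallowed doses, or one missed dose of one drug over three days.
- **Symmetry between arms.** A per-drug rule does not create it. A Coartem child missing one of six doses has 5/6 = 83.3% and stays, whereas a child missing one whole dose of KAF156 would have 50% or 66.7% and leave. This also stands. The case for a per-drug rule is that each component should have been received, not that the arms become identical.
- **Wording.** The optional plural in the PPS criterion could be read as each drug. Nothing in the SAP says so, and the cross-reference leads to the average.

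**Conclusion.** The point holds for the PPS. As written, the 80% rule admits a child with 60% of one drug when the other is complete, and one with two of three doses of one drug, to the set used for the primary test. This rests on the PPS using the 2.4.1 average, which the cross-reference supports, and on partial doses being credited in mg, as the example does. Other PPS criteria could still remove a given child.

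The likely effect is small. The documents give no count of affected children; on the illustration above, each removal moves the arm's rate by at most about 1 point, and the sign depends on the child's outcome. The weakness lies in what the PPS means and in the ambiguity of the calculation.

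The PK-set conflict is a separate inconsistency and holds whichever way compliance is averaged.

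**What to change.** 1. In SAP 2.2 and Table 5-14, define the PPS criterion as at least 80% of the planned dose of each of KAF156 and LUM-SDF. The combined average can stay as a descriptive summary.
2. In SAP 2.4.1, make the formula agree with the example by stating whether partly taken doses count in mg or only doses taken in full.
3. Reconcile the PK-set threshold between SAP 2.2 and protocol 12.1 (at least 80%) and Table 5-14 (below 100% excluded). Apply the one kept per drug, because PK is summarised separately for KAF156 and lumefantrine.

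The cost is SAP wording; per-drug compliance is already calculated, so no new data are needed. A few children may leave the PPS from the KAF156/LUM-SDF arm only, which could slightly favour that arm. The change should therefore be fixed before outcomes by arm are known, and exclusions for this reason should be counted. The FAS analysis in SAP 2.5.4 has no compliance cut-off and still includes these children.

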2.4.2 Prior, concomitant and post therapies

Prior and concomitant medications will be summarized in separate tables by treatment group.

Concomitant rescue and other anti-malarial medications will also be summarized by treatment group.

Note – rescue medications and non-study antimalarial drugs are the same. If they are used after discontinuation of study drug due to early treatment failure, late clinical failure or late parasitological failure then they should be considered as rescue medications, otherwise, they are considered as other non-study drug antimalarial medications. Rescue medications will be

captured along with other concomitant medications by the investigators under rescue medication category.

Prior medications are defined as drugs taken and stopped prior to first dose of study medication. Any medication given at least once between the day of first dose of study medication and the last day of study visit will be a concomitant medication, including those which were started pre-baseline and continued into the treatment period.

Prior and concomitant medications will be coded according to the latest version of WHO Drug Reference List dictionary which employs the ATC. The number and percentage of patients taking prior and concomitant medications will be summarized for each treatment by ATC class and preferred term (PT).

Number and percentages of the patients received prohibited prior and concomitant drugs will be summarized

Safety set will be used.

2.5 Analysis related to the primary objective

The primary objective is to demonstrate the non-inferiority (NI) of a KAF156 and LUM-SDF combination to Coartem[®] for treatment of uncomplicated malaria caused by *P. falciparum* in children 6 months to < 12 years old. The NI margin (Δ) has been set to 10%.

Patients from Cohorts 1 and 2 will be pooled together. In case that Cohort 2 stops early, such as after the first 24 patients, the study objectives will be assessed based on Cohort 1 data alone since there will be enough statistical power for Cohort 1 alone (refer to Section 3.1.1) while Cohort 2 will be analyzed mainly using descriptive statistics.

2.5.1 Primary endpoint

The primary efficacy variable is the PCR corrected Adequate Clinical and Parasitological Response (ACPR) at Day 29 (i.e. 28 days post-dose) (see [Section 2.1](#)) (Cohorts 1 and 2 pooled).

2.5.2 Statistical hypothesis, model, and method of analysis

The statistical null hypothesis is that the difference in PCR-corrected ACPR rate at Day 29 between KAF156 and LUM-SDF combination and Coartem[®] is at most -10% with the alternative hypothesis that it is greater than -10%. The statistical hypothesis will be evaluated using the lower limit of two-sided 95% confidence interval (CI) for the difference between two treatment groups.

If Cohort 2 does not stop early, two-sided 95% CI for the difference between two treatment groups will be provided for Cohorts 1 and 2 pooled using Mantel-Haenszel estimate of the common risk difference stratified by cohort (see [SAS manual version 13.2 Pages 2681-2682, 2014](#)). If the lower limit of 2-sided 95% CI for the difference is greater than -10%, the null hypothesis will be rejected.

In case that Cohort 2 stops early, such as after the first 24 patients, two-sided 95% CI for the difference between two treatment groups will be provided for Cohort 1 alone using the Wilson

uncorrected method. If the lower limit of 2-sided 95% CI for the difference is greater than -10%, the null hypothesis will be rejected.

The statistical hypothesis testing will be evaluated based on the PPS.

2.5.3 Handling of missing values/censoring/discontinuations for primary endpoint analysis

Parasite assessments obtained within the visit window for Day 29 (Day 25 to Day 33) will be considered as the assessment for Day 29.

No missing data are expected for the primary efficacy analysis based on PPS since patients who are not evaluable for the primary efficacy variable are excluded from PPS. See [Section 2.5.4](#) for missing data handling for the supportive analysis using FAS.

2.5.4 Sensitivity analyses

- The primary efficacy analysis will be repeated on the FAS using the statistical methods specified in [Section 2.5.2](#). Primary efficacy variable will be handled additionally for those patients who are excluded from the PPS as follows:
 - Presence of parasitaemia which cannot be determined to be recrudescence or new infection due to missing PCR data will be counted as non-responders (from the day of test)
 - Missing/undetermined responses at Day 29 due to missing blood smear data at the visit will be counted as non-responders unless there is a later blood smear test indicating no parasitemia.
 - Patients with new infection before Day 29 will be considered 1) not achieving PCR-corrected ACPR at Day 29 in one analysis and 2) and achieving PCR-corrected ACPR at Day 29 in another analysis
 - Patients who received non-study related anti-malarial medication without having reappearance of the parasites will be considered in the analysis as if they had not taken these drugs. This is because such cases will be very unlikely as administration of such medicines are expected only in case of the reappearance of the parasites. Note- Patients who take non-study anti-malarial medication due to repeated vomiting of study medication should be considered as treatment failure.

Note: These patients did not experience any treatment failure (ETF, LCF, or LPF). In case that non-PPS patients who experienced treatment failure, they will be included as non-responders if they received rescue medication for the treatment of *P. falciparum* malaria due to recrudescence or as responder for PCR corrected ACPR if they received rescue medication to treat a new infection on Day 29 visit.

- Patients who received non anti-malaria medication with potential anti-malarial activity without having reappearance of the parasites will be considered in the analysis as if they had not taken these drugs. This is because such medications will have minimal effect on efficacy.

- Although the objective of Run-in cohort is to investigate the food effect on bioavailability of KAF156 and lumefantrine, analyses related to primary and other secondary variables will be performed in Run-in cohort by treatment group, unless otherwise specified.

2.5.4.1 Analysis of PCR-corrected ACPR rate using Kaplan-Meier method

For the FAS, the proportion of patients with PCR-corrected ACPR at Day 29 and 95% CI will be also estimated using the Kaplan-Meier method ([Stepniewska and White 2006](#) and [WHO 2015](#))

Event = PCR-corrected non-responder during the study (same as at Day 15, Day 43, see [Section 2.1](#)). The event time is the first time when the patient becomes a non-responder based on PCR-correction. If a patient parasite is not cleared at all, Day 7 is considered as the event time.

The PCR-corrected responder rate at Day 29 is estimated by the survivor function at Day 29 using the Kaplan-Meier method.

Rule for censoring:

The following censoring rules will be applied to the patients who were not non-responder

- Patients who had a new infection with *P. falciparum* or other species without *P. falciparum* recrudescence on or after Day 8 will be censored at the first time of the PCR that indicate the infection or blood smear with other species.
- Patients who received non-rescue antimalarial medication for other infections [REDACTED] will be censored at the first time of antimalarial medication.
- Patients who have parasites at Day 8 or later but cannot be determined as recrudescence or new infection due to missing PCR genotyping will be censored at the time of the first malaria blood film with presence of parasites on or after Day 8.
- Other patients not classified as non-responder will be censored at the time of last parasitemia assessment.

An asymptotic two-sided 95% CI for the difference in proportion of responders between two treatment groups will be calculated from the z-test statistic distribution based on the variance of individual proportion using the Greenwood formula.

The confidence interval will be constructed as: $(r_k - r_c) \pm Z_{\alpha/2} * SE_d$;

where,

r_k = Kaplan-Meier estimate for the treatment group at time t,

r_c = Kaplan-Meier estimate for the control group at time t,

$SE_d = \sqrt{(SE_k^2 + SE_c^2)}$,

SE_k = estimated standard error for the treatment group based on Greenwood's formula,

SE_c = estimated standard error for the control group based on Greenwood's formula,

$Z_{\alpha/2}$ = z-statistic = probit(1- α /2) from a normal distribution function, $\alpha = 0.05$.

